##### **6.5.1 Study Duration for Subjects**

The estimated study duration for a participant is 12 months, approximately 4 weeks for screening and 10 months of treatment. However, this may be longer or shorter depending on the subject's disease, ability to tolerate study treatment and/or willingness to participate in the study. Approximately 30 days after the last dose of oprozomib, the subject will return to the clinic for a safety follow-up (EOS) visit.

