##### **6.5.2 End of Study**

The end of study for a subject occurs when a subject discontinues study treatment and completes the EOS visit. The date the final safety assessment or procedure is performed is considered the end of study. The safety follow-up or EOS visit will occur 30 to 37 days after the last administration of study treatment. A subject is considered to have completed the study if they complete an EOS visit.

Primary Completion: is defined as the time when the last subject is assessed or receives an intervention for the purposes of final collection of data for the primary

analysis. The primary analysis will occur when target enrollment is complete and each subject either completes 2 months on study or withdraws from the study. Subjects who are still active at the time of the primary analysis may continue on study treatment until disease progression, study withdrawal, death, or intolerance to study treatment is observed.

End of Study: is defined as the time when the last subject is assessed or receives an intervention for evaluation in the study. Once achieved, the final analysis will occur.

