### **9.2 Investigational Product**

All investigational product(s) will be self-administered. A diary will be provided for subjects to record their adherence to the oral medication. Time of meal intake will be

recorded on subject diary for dosing days at home. For purposes of this protocol, “study treatment” refers to any combination of oprozomib, pomalidomide and dexamethasone.

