Treatment will continue until disease progression, unacceptable toxicity, or study treatment (**oprozomib**) discontinuation for any reason.

The effects of overdose of oprozomib are not known.

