### 9.3.2.2 Dosage Adjustments, Delays, Rules for Withholding or Restarting, Permanent Discontinuation

[figure not shown]
If any dose of pomalidomide, oprozomib or dexamethasone is reduced during the previous cycle, the reduced dose level will be continued on day 1 of the next cycle. If the reduced dose level is well tolerated for a complete cycle, the subject may, at the investigator's discretion, be re-challenged with the dose level prior to the reduction at the start of the next cycle unless the subject experiences a GI hemorrhage.

In addition to dose reductions, administration of oprozomib, pomalidomide and dexamethasone may be temporarily interrupted for a maximum of 4 weeks in the event of a treatment-related toxicity. If the dose delay because of toxicity is longer than 4 weeks, the subject will be discontinued from study treatment. If a subject misses more than 4 consecutive weeks for reasons other than toxicity after completing cycle 1, the subject will be discontinued from study treatment unless it is determined that the subject was benefiting from therapy and the Amgen study medical monitor permits the subject to resume therapy.

[figure not shown]
Dexamethasone will be permanently discontinued after 2 dose reductions for either nominal dose in the event of additional dexamethasone-related toxicity. At the investigator's discretion, dexamethasone may be tapered prior to complete discontinuation according to institutional practice. If dexamethasone dosing is permanently stopped due to toxicity in accordance with the dose modification guidelines described in [Table 5](#), the subject may continue to receive oprozomib and pomalidomide, and will continue to follow protocol required therapy, procedures, and assessments. Subjects may continue to take antiemetic doses of dexamethasone (4 mg) on days of oprozomib dosing, if tolerated, at the investigator's discretion. In the event pomalidomide is permanently discontinued, oprozomib in combination with dexamethasone may be continued. Similarly, if oprozomib is discontinued, pomalidomide and dexamethasone may be continued. Please see the diagram Guidelines for Oprozomib and Pomalidomide Dose Modifications and Treatments.

[figure not shown]

a The maximum allowed dose interruption is 4 weeks for treatment-related toxicity.

[figure not shown]

a The maximum allowed dose interruption is 4 weeks for treatment-related toxicity.

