#### 10.2.19 Treatment

The following procedures will be completed during the treatment period at the times designated in the Schedule of Assessments ([Table 6](#)). Study treatment is to be administered after all protocol-specific pre-dose assessments have been performed during each visit that it is required. A +/-1 day window is allowed for C1D8, C1D15, C1D22, C2D15, C3D15 and C4D15, however study treatment dosing must occur on two sequential days. Starting with C2, there is a +/-2 day window for D1 of every cycle. Subjects may continue on treatment until disease progression, unacceptable toxicity, or study treatment discontinuation for any reason.

- Clinical evaluation which includes physical examination with neurological assessment and ECOG performance status
- Peripheral neuropathy assessment
- Adverse event assessment
- Documentation of concomitant medications
- Vital signs (blood pressure, respiratory rate, heart rate, temperature)
- 12-lead ECG in triplicate (only performed if clinically indicated after cycle 2)
  - collected in the supine position after subject has rested for 5 minutes
  - record QRS, QT, QTc, RR and PR intervals
- Pregnancy test – serum or urine (only for females of childbearing-potential)
- Safety laboratory assessments (locally tested)
  - Chemistry
  - Hematology

- Coagulation
- Urinalysis
- Blood collection
  - Oprozomib PK
  - [REDACTED]
- Disease assessments
  - SPEP
  - 24-hour urine protein electrophoresis (UPEP)
  - Immunofixation if required
  - sFLC
  - Quantitative immunoglobulin if clinically indicated
- Imaging assessments
  - Plasmacytoma (only to confirm a response of PR or better, to confirm PD, or if clinically indicated)
  - Bone lesions (every 8 weeks if clinically indicated)
- Dexamethasone dosing (taken with food or after meals, may be taken with oprozomib)
- Oprozomib dosing: IR formulation recommended to be taken after a low fat meal. The GR formulation must be taken immediately after a main meal that contains the highest calorie and fat content.
- Pomalidomide dosing (may be taken with or without food) for all subjects except for subjects during cycle 1 in Part 1

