It is defined as the first day that protocol specified study treatment is administered to the subject.

Study Day

Post study day: study day= (date - date of Study Day 1) + 1

Pre study day: study day= (date – date of Study Day 1)

Time to Response (TTR)

Time to response defined as the interval from the first administration of study treatment to the first documentation of confirmed response. Response is defined as any of the following: stringent complete response (sCR), complete response (CR), very good partial response (VGPR), or partial response (PR) (all according to Revised International Myeloma Working Group Uniform Response Criteria [IMWG-URC]).

Time to response is calculated as the number of days:

(date of first response – date of study day 1 +1).

Time to response will be calculated only for subjects with response.

Treatment-Emergent Adverse Event (TEAE)

Treatment-emergent adverse events are events categorized as Adverse Events (AEs) **starting on or after first dose of investigational product as determined by the flag indicating if the adverse event started prior to the first dose on the Events CRF and up to and including 30 days after the last dose of investigational product or the End of Study date, whichever is earlier.**

Treatment-Related AE

A treatment-related AE is any treatment-emergent AE that per investigator review has a reasonable possibility of being caused by study treatment.

Disease-Related Events

Disease-Related Events are events (serious or non-serious) anticipated to occur in the study population due to the underlying disease.

C_{max}

Maximum observed serum concentration.

t_{max}

Time to C_{max}

AUC_{last}

Area under the concentration-time curve from time 0 (time of investigational product administration) to the time of the last quantifiable concentration.

Progression free survival

The number of months from subject's first study dose date to the earlier of disease progression or death due to any cause.

Progression free survival data will be censored as described below:

- **Patients who are alive and do not have documented disease progression at the time of analysis will be censored at the date of the last disease assessment.**
- **Patients who are alive and do not have disease assessment at the time of analysis will be censored at the first study dose date.**

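### The rules for treatment end and follow-up conflict on whether they run from oprozomib or from all study treatment, and the SAP's oprozomib-only window can leave regimen-related events out of the primary safety endpoint.

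*Protocol*

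**What the plan says.** **Treatment end.** Protocol Section 9.2.1.1: "Treatment will continue until disease progression, unacceptable toxicity, or study treatment (oprozomib) discontinuation for any reason". Section 9.3.2.2: "Similarly, if oprozomib is discontinued, pomalidomide and dexamethasone may be continued". Section 10.2.19 restates the stopping rule without naming oprozomib: "Subjects may continue on treatment until disease progression, unacceptable toxicity, or study treatment discontinuation for any reason". Section 9.2 says that study treatment "refers to any combination of oprozomib, pomalidomide and dexamethasone".

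**Follow-up visit.** Section 6.5.1: "Approximately 30 days after the last dose of oprozomib, the subject will return to the clinic for a safety follow-up (EOS) visit". The footnote to the Part 1 schema agrees with it. Section 6.5.2: "The safety follow-up or EOS visit will occur 30 to 37 days after the last administration of study treatment". Section 10.2.20 also counts from the last study treatment, and footnote 19 to the Schedule of Assessments counts from the last dose of study drug.

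**Event collection.** Section 12.2.2.1 collects non-serious adverse events from the first dose of study treatment to the end-of-study visit. Section 12.2.2.2 gives the end of serious-event collection as 30 days after investigational-product dosing and as the end-of-study visit, joined by a slash.

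**Safety analysis.** SAP Section 5 defines investigational product as oprozomib alone. It counts an event as treatment-emergent "up to and including 30 days after the last dose of investigational product or the End of Study date, whichever is earlier". A treatment-related event must first be treatment-emergent, and its causality is judged against study treatment, which covers all three drugs. Incidence of treatment-related, treatment-emergent events is a primary endpoint (Protocol Section 13.1.1).

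**Efficacy analysis.** SAP Section 5 runs PFS from the first dose to progression or death and censors for new anti-cancer therapy only when it lies outside study treatment. Best overall response is taken over the whole study. Duration of response has no cut at the last oprozomib dose.

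**The concern.** A site whose subject stops oprozomib cannot follow both Section 9.2.1.1 and Section 9.3.2.2, and cannot tell from Sections 6.5.1 and 6.5.2 when the end-of-study visit is due.

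The analysis inherits the conflict. If pomalidomide and dexamethasone continue, the primary safety endpoint stops counting 30 days after the last oprozomib dose, while the subject is still receiving two drugs of the regimen. The response and PFS rules count that same period as time on study treatment. Safety and efficacy would then describe different stretches of exposure for the same subjects, and both feed the recommendation of a dose and formulation. At stake is what the primary safety tables count, and whether a reader can set them beside the efficacy results.

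**Working it through.** The plan states no figure for this issue, so the check is a comparison of texts, with arithmetic for context only.

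**Step 1: combine the rules.**

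| Treatment rule | Visit timed from | Consequence |
|---|---|---|
| 9.2.1.1 (ends with oprozomib) | last oprozomib (6.5.1) | Safety and disease assessments could end together about 30 days later. Little or no mismatch. |
| 9.2.1.1 | last study treatment (6.5.2, 10.2.20) | Nearly the same, since treatment ends with oprozomib. |
| 9.3.2.2 (two drugs may continue) | last study treatment | Events are collected to the visit (12.2.2.1), and all adverse event data are listed (Protocol 13.3.2, SAP 7.2). Those starting more than 30 days after the last oprozomib dose are not treatment-emergent. |
| 9.3.2.2 | last oprozomib | Scheduled event collection and disease assessment could both end at that visit while two drugs are still permitted. |

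**Step 2: trace one event through the third row.** Suppose that a pomalidomide-related event starts 45 days after the last oprozomib dose, before the end-of-study visit. The SAP takes the earlier of two dates, so a later visit does not lengthen the window. Since 45 > 30, the event is not treatment-emergent and so cannot be treatment-related under the SAP. It is collected and listed but absent from the primary endpoint, although its causality would be judged against a regimen that includes pomalidomide.

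**Step 3: trace efficacy for the same subject.** Pomalidomide plus dexamethasone is a combination within study treatment, so continuing it does not censor PFS. A best response first reached in this period counts.

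**Step 4: how many subjects?** Table 2 of the protocol gives OPomd subjects with an adverse event leading to discontinuation of investigational product: IR 150 mg 1/4, GR 150 mg 1/4, IR 200 mg 2/8, GR 200 mg 1/5, IR 225 mg 0/10, IR 250 mg 1/8. The total is 6/39 = 15.4% (exact 95% CI 5.9% to 30.5%). How many of the six continued pomalidomide and dexamethasone is not stated. Subjects who stopped oprozomib for other reasons are not in this count.

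**Step 5: how much time per subject?** Assume k further 28-day cycles of two drugs, each moving the last dose by 28 days, and a visit 30 days after the last study treatment. Follow-up after the last oprozomib dose is 28k + 30 days, of which the treatment-emergent window covers 30. The share outside is 28k / (28k + 30).

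| k (assumed) | Follow-up, days | Outside window, days | Share |
|---|---|---|---|
| 0 | 30 | 0 | 0% |
| 1 | 58 | 28 | 48% |
| 2 | 86 | 56 | 65% |
| 4 | 142 | 112 | 79% |
| 8 | 254 | 224 | 88% |

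The documents give no value for k. The table shows how the gap scales for one subject, not how large it was in the trial.

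**The case against.** A reader might infer that later toxicity is lost. The documents do not support that in general. Sections 6.5.2 and 10.2.20 time the visit from the last study treatment, Section 12.2.2.1 collects events up to it, and the listings cover all adverse event data. On that reading the events are missing only from the treatment-emergent tables. On the reading that ends both treatment and follow-up with oprozomib, there is no long two-drug period to miss. This objection stands and limits the point to tabulation and conflicting anchors.

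A reader might also infer that the mismatch favours OPomd in choosing a dose and formulation. That is not shown. The MTD rests on DLTs, assessed mainly in the first 28 days. The dose level review team sees all available data, including data after the DLT window. The discontinuation counts do not rise with dose. The study has no control arm and describes its analyses as hypothesis generating.

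Nor can several months of efficacy be assigned to the two drugs from the 4.0-month median PFS in Section 5.5.4.3. That figure comes from another trial's pomalidomide and low-dose dexamethasone arm. It does not describe remaining PFS in subjects who drop oprozomib partway through treatment.

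Finally, both analysis choices can be defended. Following PFS through continued components of the regimen is a legitimate treatment-policy choice. Anchoring adverse events to the investigational product keeps oprozomib dose attribution clear in a dose-finding study. This stands against replacing the main efficacy analysis or discarding the oprozomib-anchored table. It does not answer the contradictions in the text, or the SAP's use of oprozomib for the window and all three drugs for relatedness.

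**Conclusion.** The point holds in a limited form. Sections 9.2.1.1 and 9.3.2.2 contradict each other. So do Section 6.5.1 with the Part 1 schema footnote, on one side, and Sections 6.5.2 and 10.2.20 on the other. If continuation is permitted, the SAP excludes from the primary safety endpoint any event related to pomalidomide or dexamethasone that starts more than 30 days after the last oprozomib dose, while PFS and best response carry on through that time.

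The size is unknown. The 6/39 shows that oprozomib discontinuation for adverse events occurred, not that anyone then continued on two drugs. The exclusion rests on the assumption that at least some did. No direction of bias in the dose or formulation recommendation is established. The correction should be made because it is cheap and changes what a primary endpoint counts.

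**What to change.** 1. Reconcile Section 9.2.1.1 with Section 9.3.2.2, and the Part 1 schema footnote and Section 6.5.1 with Sections 6.5.2 and 10.2.20. Which treatment rule applies is for the sponsor to decide.
2. State one anchor for the end-of-study visit, adverse and serious adverse event collection (Sections 12.2.2.1 and 12.2.2.2) and the SAP's treatment-emergent window.
3. If pomalidomide and dexamethasone may continue, run the treatment-emergent window to 30 days after the last dose of any study treatment. Keep the oprozomib-anchored table as a supplement so that dose attribution stays visible.
4. Optionally, add sensitivity analyses of best overall response, PFS and duration of response cut at oprozomib discontinuation, without replacing the main analyses.

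The cost is protocol wording, one changed SAP definition and a few extra tables. The protocol already reports tables on the present definition, with a cutoff of 02 December 2019, so the change would mainly affect the final analysis, which reuses the primary-analysis methods.

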**Additional guidance regarding hematologic toxicities and dosing actions is as follows:**

- To initiate a new cycle of pomalidomide, the ANC must meet the criteria in the regional prescribing information. If toxicities continue to occur after dose reductions down to 1 mg, discontinue pomalidomide.
- Non-treatment-related events: if the toxicity resolves to  $\leq$  Grade 1 or baseline and the toxicity is not treatment-related, oprozomib may be restarted at the same dose level
- If required by continued or recurrent toxicity, a second or third dose reduction of oprozomib may be permitted after discussion with the Amgen medical monitor. No more than 3 dose reductions will be permitted for an individual subject on study and additional reductions may be managed by schedule change. If toxicity continues, oprozomib should be discontinued.

**Additional guidance regarding nonhematologic toxicities and dosing actions is as follows:**

- Non-treatment-related events: If the toxicity resolves to  $\leq$  Grade 1 or baseline and the toxicity is not treatment-related, oprozomib may be restarted at the same dose level
- If the subject tolerates the reduced dose for 1 cycle, the subject's dose may be re-escalated to the dose being taken prior to the dose reduction after discussion with the Amgen medical monitor
- If required by continued or recurrent toxicity, a second or third dose reduction of oprozomib may be permitted after discussion with Amgen medical monitor. No more than 3 will be permitted for an individual subject on study and additional reductions may be managed by schedule change. If toxicity continues, oprozomib should be discontinued.
- Subjects who develop Grade 3 or 4 GI hemorrhage should not be re-challenged with oprozomib. Oprozomib should be permanently discontinued. Endoscopy should be strongly considered for any subject with GI hemorrhage.

Guidelines for dexamethasone dose modifications and treatment are summarized in **Table 5**.

**Table 5. Guidelines for Dexamethasone-Related Toxicity**

Body System	Symptom	Recommended Action
Gastrointestinal	Dyspepsia, gastric or duodenal ulcer, or gastritis Grade 1 or 2 (requiring medical management)	Continue dexamethasone at same dose and treat with therapeutic doses of H2 blockers, or proton pump inhibitor. May consider adding sucralfate or other antiulcer treatment as clinically indicated. If symptoms persist despite above measures, decrease dexamethasone dose by 1 dose level.
	Dyspepsia, gastric or duodenal ulcer, or gastritis $\geq$ Grade 3 (requiring hospitalization or surgery)	Hold dexamethasone until symptoms return to baseline. Restart dexamethasone at 1 dose decrement along with concurrent therapy with H2 blockers, sucralfate, or omeprazole. If symptoms persist despite above measures, discontinue dexamethasone permanently.
	Acute pancreatitis	Permanently discontinue dexamethasone.
General Disorders	Edema $>$ Grade 3 ( $>$ 30% limb discrepancy in volume; gross deviation from normal anatomic contour; limiting self-care activities of daily living)	Hold dexamethasone until symptoms return to baseline. Administer diuretics as needed, and restart dexamethasone at 1 dose decrement; if edema persists despite above measures, decrease dose another level. Discontinue dexamethasone permanently if symptoms persist despite second reduction.
Psychiatric Disorders	Confusion or mood alteration $\geq$ Grade 2 (interfering with function $\pm$ interfering with activities of daily living)	Hold dexamethasone until symptoms return to baseline. Restart dexamethasone at 1 dose decrement. If symptoms persist despite above measures, reduce by another dose decrement.
Musculoskeletal	Muscle weakness $\geq$ Grade 2 (symptomatic and interfering with function $\pm$ interfering with activities of daily living)	Hold dexamethasone until symptoms return to baseline. Restart dexamethasone at 1 dose decrement. If weakness persists, decrease dose by 1 more dose level. Discontinue dexamethasone permanently if symptoms persist.

Page 1 of 2

**Table 5. Guidelines for Dexamethasone-Related Toxicity**

Body System	Symptom	Recommended Action
Metabolism and Nutrition Disorders	Hyperglycemia $\geq$ Grade 3 (fasting glucose $> 250$ mg/dL)	Hold dexamethasone until glucose is $\leq$ Grade 2 ( $< 250$ mg/dL) and treat with insulin or other hypoglycemic agents as needed. If uncontrolled despite above measures, decrease dose by 1 dose level until $\leq$ Grade 2 ( $< 250$ mg/dL)
All Other	Other nonhematologic toxicity $\geq$ Grade 3 felt related to dexamethasone	Hold dexamethasone dose. Resume at 1 dose decrement when toxicity has resolved to Grade 2 or less or to baseline. If toxicity recurs, hold dexamethasone dose until toxicity has resolved to Grade 2 or less or to baseline and resume dexamethasone dose by 1 more dose decrements. If toxicity recurs despite 2 dose decrements, discontinue dexamethasone permanently.

Page 2 of 2

#### **9.4 Management and Prophylaxis of Additional Adverse Events of Interest**

##### **9.4.1 Herpes Zoster Infection**

Valacyclovir or an equivalent antiviral is recommended for the duration of treatment to decrease the risk of reactivation of Herpes zoster.

